10.2. Missing Data

Missing data will be prospectively minimized through training of the participating investigator and site staff, and through appropriate clinical trial management. Every effort will be made to collect all data points in the study. All patient data that is available on patients who drop out during the course of the study will be included where possible. Sensitivity analyses will be conducted to determine the effect of missing data on the primary efficacy endpoint.

10.3. Analysis Populations

All primary efficacy analyses will be performed on all treated tumors with a Galil Medical Cryoablation System and needles as intent-to-treat population. A supplemental per-protocol analysis will be done for the primary efficacy endpoint, removing index tumor which did not have a complete treatment and/or those that did not meet the study criteria but were enrolled.

The intent-to-treat and per-protocol analyses will be compared for level of agreement. It is expected that the two tumor populations will be similar; however, any substantial differences between the two will be analyzed appropriately to elucidate the cause of these differences.

10.4. Poolability

Poolability of results across sites will also be addressed to determine if differences exist among the primary efficacy and safety endpoints and to determine if potential predictive covariates differ. For this poolability analysis, low enrolling centers may be combined into virtual center(s). Tests for comparability in terms of the primary efficacy endpoint and in terms of variables such as gender, medical history, and risk factors will be assessed.

10.5. Analysis

10.5.1. Software

Version 9.2 or higher of the SAS® statistical software package or other widely accepted statistical software will be used to provide all statistical analyses.

10.5.2. General Analysis

Data will be analyzed using descriptive statistics. Continuous variables (e.g., age) will be summarized by the number of patients, mean, standard deviation, median, interquartile range, minimum and maximum. Categorical variables (e.g., race) will be summarized by frequencies and percentages of patients in each category. 95% confidence intervals will be calculated as appropriate.

10.5.3. Primary Endpoint

The primary endpoint for this study is defined as follows: efficacy of cryoablation on local tumor control for each index tumor in patients with pulmonary metastatic disease at 12 months post cryoablation.

Patients are allowed up to 6 tumors and the primary efficacy endpoint (tumor control) will be calculated on a per tumor level. To be considered a success each tumor treated during the baseline procedure must meet the tumor control criteria at the 12 month follow-up visit.

The local tumor control counts and rates will be presented along with the 95% two-sided confidence intervals for the rates. The rate numerator will be defined as the number of tumors experiencing tumor control at 12-months. The rate denominator will be defined as the total number of tumors evaluated at 12-months.

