Analysis Populations

All primary analyses will be performed on all tumors with a Galil Medical Cryoablation System and needles as the intent-to-treat evaluable population. A supplemental per-protocol analysis

will be done for the primary endpoint, removing tumors that 1) did not have a complete treatment; and subjects who 2) did not meet the study criteria but were enrolled; or 3) had a deviation with high likelihood of affecting the study outcome (as determined by a review of all occurring deviations).

The intent-to-treat and per-protocol analyses will be compared for level of agreement. It is expected that the two populations will be similar; however, any substantial differences between the two will be analyzed appropriately to elucidate the cause of these differences. Missing data will be imputed for the primary analysis as outlined in section "Handling of Missing Data" section later in the SAP. Additional sensitivity analyses using alternate missing data imputation will be presented.

Efficacy Endpoint Analysis

Efficacy Endpoint

The primary efficacy endpoint for this study is assessment of cryoablation on local tumor control in patients with pulmonary metastatic disease at 12 months post cryoablation.

Analysis Methods

The primary efficacy endpoint for this study is defined as follows: local tumor control in patients with pulmonary metastatic disease at 12 months post cryoablation. Tumor control will be defined by the criteria defined in Section 9.7 of this protocol.

Patients are allowed up to 6 tumors and the primary efficacy endpoint (tumor control) will be calculated on a per tumor level.

The rate of local tumor control at 12-months will be analyzed using a random effects logistic regression model accounting for within subject correlation to account for multiple tumors per subject. The null hypothesis will be tested comparing the lower bound of the Wald 97.5% one-sided confidence interval for the estimated rate of local tumor control to the performance goal of 84.0%. If the lower bound is greater than 84.0%, the null hypothesis will be rejected and the endpoint will be considered met.

Safety Endpoint Analysis

Safety Endpoint

The safety endpoint for this study is to assess the incidence and severity of cryoablation related adverse events.

Analysis Methods

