For the formal primary endpoint hypothesis test, patients with missing 12-month tumor evaluations will be imputed using multiple imputation (SAS PROC MI using FCS logistic regression and including tumor status at prior visits), except in the following case where previous visit evidence can be used to impute 12-month status:

- Subjects with local tumor failure at 6-months will be considered a local tumor failure at 12-months post-index procedure.

Additional sensitivity analyses to be conducted:

- Worst case: all missing data are imputed to be failures
- Best case: all missing data are imputed to be successes
- Complete case: all missing data are treated as missing and not imputed

Subset Analyses

Analysis will be done on outcomes for subgroups including, but not limited to, gender and lesion size. Additional non-protocol defined subgroups include: number of needles used, number of lesions, primary cancer diagnosis, and lesion location.

Poolability Analyses

A poolability analysis among investigational centers and geographies (US/OUS) will be performed for the primary efficacy endpoint. This analysis will be performed on the ITT population.

Poolability of Sites

Combining of Small Sites

Sites contributing less than 5 subjects to the as treated analysis set will be considered “small sites” and ordered by the date of first enrollment in the as treated analysis set. Starting with the first “small site”, a pseudo-site will be created by adding subjects from successive “small sites”. If the number of subjects reaches or exceeds the size of the median enrollment of the “large sites”, then a second pseudo-site will be created. Additional pseudo-sites, if needed, would be created in the same manner.

Primary Endpoint by Site

Among sites and pseudo-sites, the proportions of subjects who achieve local tumor control at 12 months will be compared using logistic regression. If the resulting p-value is ≤ 0.05 , further exploratory analysis will attempt to identify covariates (baseline characteristics) that may explain differences among the sites. Otherwise, the data will be considered to be poolable across study sites.

Poolability of Geographies

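### Protocol 10.5.3 defines the primary rate over tumors evaluated at month 12, which conflicts with the all-treated population in 10.3 and with the imputed analysis that the SAP actually tests

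*Protocol*

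**What the plan says.** Protocol 10.5.3 (Primary Endpoint) counts tumors with control at 12 months in the numerator and then says: "The rate denominator will be defined as the total number of tumors evaluated at 12-months". Results are to be shown with two-sided 95% intervals.

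Protocol 10.3 (Analysis Populations) says: "All primary efficacy analyses will be performed on all treated tumors with a Galil Medical Cryoablation System and needles as intent-to-treat population". It contains no imputation rule. Protocol 10.2 (Missing Data) offers only this: "Sensitivity analyses will be conducted to determine the effect of missing data on the primary efficacy endpoint". The decision rule in Protocol 10.1 is an exact one-sided 97.5% lower bound above 84.0%.

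The SAP, under Analysis Populations, says: "All primary analyses will be performed on all tumors with a Galil Medical Cryoablation System and needles as the intent-to-treat evaluable population". It adds: "Missing data will be imputed for the primary analysis as outlined in section", pointing to Handling of Missing Data. That section says: "For the formal primary endpoint hypothesis test, patients with missing 12-month tumor evaluations will be imputed using multiple imputation". It makes one exception, which is fixed as failure: "Subjects with local tumor failure at 6-months will be considered a local tumor failure at 12-months post-index procedure". The observed-case version appears there only among the sensitivity analyses: "Complete case: all missing data are treated as missing and not imputed".

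**The concern.** The protocol gives the primary endpoint two bases: all treated tumors in 10.3, and only those with a month-12 evaluation in 10.5.3. The second drops every tumor whose patient died, withdrew or missed the scan. Apart from the carry-forward of 6-month failures, it is what the SAP demotes to a sensitivity analysis.

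The missing tumors may not be a random subset. Protocol 7.8 withdraws a patient whose index tumor receives another local treatment, and Protocol 7.9 records hospice entry as early termination. If such tumors have worse local control, an evaluated-only rate is too high. A reader working from the protocol alone would also apply the exact bound of 10.1 to the 10.5.3 fraction, because no other protocol text supplies a numerator and a denominator. That reader could reach a different answer on the trial's only hypothesis test from someone following the SAP.

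**Working it through.** **Inputs.** From Protocol 10.1 and the SAP's Sample Size Justification: P0 = 0.84, P1 = 0.91, one-sided alpha 0.025, N = 203, success if R ≥ 181, actual alpha 0.0239, power 0.8501, 10% attrition, 226 tumors. The control rate among tumors without a month-12 evaluation is not in the documents and is assumed below.

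**Step 1: reproduce the plan's figures** (exact binomial, independent tumors).
- P(X ≥ 181 | 203, 0.84) = 0.0239 and P(X ≥ 181 | 203, 0.91) = 0.8501. A cut-off of 180 would give 0.0384, so 181 is right.
- 203 / 0.90 = 225.6, rounded up to 226. The 203 is therefore a count of evaluated tumors, with 226 − 203 = 23 missing.

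**Step 2: same outcomes, different denominators** (exact one-sided 97.5% lower bound; goal met if above 84.0%).

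| Tumors counted | Rate | Lower bound | Goal |
|---|---|---|---|
| 181/203, evaluated only | 89.2% | 84.05% | met |
| 181/204, adding one unevaluated 6-month failure | 88.7% | 83.6% | missed |
| 181/226, all 23 missing as failures | 80.1% | 74.3% | missed |
| 201/226, 20 of 23 missing as controlled | 88.9% | 84.1% | met |
| 204/226, all 23 missing as controlled | 90.3% | 85.6% | met |

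The second row isolates the carry-forward rule; the other 22 missing tumors are left out of it. On all 226 tumors the cut-off is 201, because 200/226 has a lower bound of 83.6%. Starting from 181 successes, at least 20 of the 23 missing tumors (87%) must count as controlled.

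**Step 3: bias of an evaluated-only test under assumed values.** Let m be the share missing and c the control rate among the missing, and fix the true all-treated rate at 0.84. Then:

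evaluated rate = (0.84 − m·c) / (1 − m)

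With m = 0.10, the planned attrition:
- c = 0.84: (0.84 − 0.084)/0.9 = 0.840; P(X ≥ 181 | 203) = 2.4%.
- c = 0.75: (0.84 − 0.075)/0.9 = 0.850; P = 5.5%.
- c = 0.70: (0.84 − 0.070)/0.9 = 0.856; P = 8.3%.

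**Limit.** Steps 2 and 3 use exact binomial bounds for independent tumors. The SAP tests a Wald bound from a random-effects logistic model after multiple imputation. That cannot be computed without a within-patient correlation and imputation data, neither of which the documents give.

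**The case against.** The strongest reply is that the SAP already fixes one method for the formal test, with its missing-data rule written expressly for that test. On this view 10.5.3 describes how rates are displayed: it speaks of two-sided intervals and states no decision rule. The protocol's design also counts evaluated tumors (203, inflated to 226), so 10.3 and 10.5.3 could be read as an observed-case plan with an intent-to-treat label. The SAP's worst-case, best-case and complete-case analyses will show how far the result depends on the missing tumors.

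Much of this stands. A reader might infer that the formal test has no settled denominator; the SAP does not support that. A reader might also take 10.3 to require imputation; it names a population only, and imputation comes from the SAP alone.

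The mismatch remains all the same. Section 10.5.3 carries the primary endpoint heading, nothing limits it to display, and it is the protocol's only definition of the fraction that the exact bound in 10.1 needs. The SAP's own population label, with its unexplained word 'evaluable', does not help to resolve it.

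**Conclusion.** The conflict is in the current text. Protocol 10.5.3 defines an observed-case rate as the primary rate, against 10.3 and against the SAP's imputed analysis. At the plan's own boundary, a single carried-forward failure changes the verdict of the exact bound (84.05% against 83.6%). That comparison needs no assumption about bias.

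The 5.5% and 8.3% rejection rates do rest on assumptions: 75% or 70% control among the missing, 10% attrition, independent tumors and an exact test on evaluated tumors. With equal control there is no inflation. A reader might infer that the trial's type I error is 8.3%, or that changing 10.5.3 restores 2.5%. Neither follows. The figures do not describe the SAP's random-effects model with imputation. That imputation draws on tumor status at earlier visits, so if missing tumors do worse in ways those visits do not show, some of the bias may remain. What the documents support is a protocol–SAP inconsistency on the primary rate that should be removed.

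**What to change.** - In Protocol 10.5.3, define the primary denominator as all treated index tumors, with missing month-12 status handled by the SAP's rule (multiple imputation, and 6-month failures counted as 12-month failures).
- In the same place, label the evaluated-only rate as the complete-case sensitivity analysis, as the SAP already does.
- In the SAP's Analysis Populations section, remove the word 'evaluable' from the population name or define it.

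The cost is about one sentence in the protocol and one word or definition in the SAP, with no new data. The downside is a headline rate that may be slightly less favourable.

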10.5.4. Safety Data

The safety data for this study will be assessed using the incidence and severity of intra-operative events, post-operative adverse events, serious adverse events and unanticipated adverse device effects related to the cryoablation procedure.

No formal hypothesis test is being made on the safety endpoints. Point estimates and two-sided 95% confidence intervals will be generated for cryoablation related adverse events.

10.5.5. Other Data Assessments

Technically successful treatment definition

A technically successful treatment will be defined by the presence of an ablation zone, ground glass opacity, or frank consolidation encompassing the targeted index tumor(s) no later than the 1 month follow up visit after the cryoablation procedure. Technical success will be analyzed on a per tumor basis.

Disease recurrence or progression definitions

The reference date for disease progression evaluation will be associated with the initial (first) cryoablation procedure done per study protocol. In the event of multiple cryoablation procedure dates, such as with bilateral lesions or staged treatments, the date of reference for disease progression evaluation will be the initial (first of n) cryoablation procedure.

- **Local disease progression** will be determined locally by evidence of local tumor failure.
- **Lung-disease-specific survival rate** is defined as the time in days from the first cryoablation procedure to death and **a)** the date of metastatic lung tumor progression (new lung tumors or local tumor failure of the index tumor), **b)** the date of death with local control of the index tumor, or **c)** the date of last follow up in patients who were still alive with local tumor control of the index tumor. Patients who are alive will be censored at the date of their last visit. Patients who have died from causes other than local failure of the index tumor will be censored at the time of death. Lung disease-specific survival rates will be summarized by using Kaplan-Meier methodology.
- **Overall survival rate** is defined as the time in days from the first cryoablation procedure to death. Patients who are alive will be censored at the date of the last visit. Overall survival rates will be summarized by using Kaplan-Meier methodology.
- **Time to metastatic lung disease progression beyond the index tumor** is defined as the time in days from the first cryoablation procedure to metastatic disease beyond the index tumor site. Patients without metastatic lung disease progression will be censored at the date of their last visit or their date of death (due to any cause). Metastatic progression free survival rates will be summarized by using Kaplan-Meier methodology.
- **Time to overall cancer progression** is defined as the time in days from the first cryoablation procedure to cancer progression (i.e., any location of active cancer disease). Patients without cancer progression will be censored at the date of their last visit or their date of death (due to any cause). Overall cancer progression free survival rates will be summarized by using Kaplan-Meier methodology.
- **Time to untreatable metastatic lung disease control with cryoablation** is defined as the time in days from the first cryoablation procedure to the time when the metastatic lung disease cannot be treated with cryoablation. Overall time to untreatable metastatic lung disease progression rates will be summarized by using Kaplan-Meier methodology.
- **Time to untreatable metastatic lung disease control with focal therapy** is defined as the time in days from the first cryoablation procedure to the time when the metastatic lung disease cannot be treated by focal (e.g., ablation, surgery, SBRT) intervention for control of metastatic lung disease. Overall time to untreatable metastatic lung disease progression rates will be summarized by using Kaplan-Meier methodology.

Intra-procedural data

Initial cryoablation procedure information including the tumor size and number, cryoablation needle type and the number of each type of needle used, freeze and thaw times, procedure times, and anesthesia type.

Physical performance and quality of life

Physical performance (KPS) and quality of life (SF-12) assessments will be made by examining the change in the baseline scores to those reported post-operatively as defined in Sections 8.4 and 8.5, respectively.

Subset Analyses

Analysis may be done on outcomes for subgroups including, but not limited to, gender, primary cancer and tumor size.

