5.3. Other Data to be Assessed

Other data for this study include, but are not limited to:

- Overall patient survival post cryoablation;
- Time to metastatic lung disease progression beyond the index tumor(s);
- Time to overall cancer progression;
- Time to untreatable metastatic lung disease control with cryoablation;
- Time to untreatable metastatic lung disease control with focal therapy;
- Efficacy of cryoablation on local tumor control for each index tumor in patients with pulmonary metastatic disease at 18 and 24 months post cryoablation;
- Efficacy of cryoablation on local tumor control for each index tumor in patients with pulmonary metastatic disease undergoing additional cryoablation treatment(s) of a previously treated index tumor;
- Cryoablation technical success (See Section 10.5.5);
- Changes in physical function and quality of life over time (See Section 10.5.5).

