6.3. Exclusion Criteria

Patients not eligible for participation in this study include patients who have any of the following:

- 6.3.1. Patient's index tumor(s) is primary lung cancer.
- 6.3.2. Patient has uncontrollable primary or metastatic disease outside of the lung.
- 6.3.3. Patient is unable to lie flat or has respiratory distress at rest.
- 6.3.4. Patient has a coagulopathy or bleeding disorder which is uncontrolled.
- 6.3.5. ANC <1000 within 8 weeks prior to initial cryoablation procedure.
- 6.3.6. Patient has evidence of active systemic, pulmonary, or pericardial infection.
- 6.3.7. Patient has a debilitating medical or psychiatric illness that would preclude giving informed consent or receiving optimal treatment or follow up.
- 6.3.8. Patient is currently participating in other experimental studies that could affect the primary endpoint (e.g. experimental chemotherapy regimen).

THE REMAINDER OF THIS PAGE IS INTENTIONALLY LEFT BLANK

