7.7. Months 6, 12, 18 and 24 – Follow-up

Patients will return 6, 12, 18, and 24 months (+/-30 days) post cryoablation procedure. In the event of multiple cryoablation procedure dates, the most recent procedure date will serve as the reference for determining the follow up visit window.

The following assessments will be completed:

- Karnofsky Performance Scale;
- Chest CT scan \pm contrast (contrast is preferred);
- Safety assessment;
- Assessment of metastatic lung disease progression beyond the index tumor and feasibility of treatment;
- Assessment of local tumor recurrence at the index tumor, including additional treatment and feasibility of treatment;
- Assessment of any systemic cancer treatment(s);
- Assessment of any local therapy for the index tumor(s).

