8.6. Imaging

The tumor(s) intended for ablation is referred to as the **index tumor(s)**. Index tumor evaluation will be conducted with the use of CT or FDG-PET-CT. The same method of assessment and the same technique should ideally be used to characterize each identified and reported index tumor at baseline and during follow-up. Imaging shall be performed with a minimum slice thickness of 5 mm and high resolution imaging is preferred with slice thickness of 3 mm or less. Three axes of measurements (longest diameter and the 2 perpendicular diameters) shall be evaluated and the longest dimension shall be used to determine the inclusion criteria. The use of contrast is preferred.

The cryoablation procedure will be completed under CT guidance. Week 1 follow-up imaging will be either chest CT or chest X-Ray. At months 1, 3, 6, 12, 18, and 24, follow up imaging will be chest CT or chest FDG-PET-CT.

The total area treated with cryoablation will be referred to as the **ablation zone(s)** in follow up imaging studies.

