- **Time to metastatic lung disease progression beyond the index tumor** is defined as the time in days from the first cryoablation procedure to metastatic disease beyond the index tumor site. Patients without metastatic lung disease progression will be censored at the date of their last visit or their date of death (due to any cause). Metastatic progression free survival rates will be summarized by using Kaplan-Meier methodology.
- **Time to overall cancer progression** is defined as the time in days from the first cryoablation procedure to cancer progression (i.e., any location of active cancer disease). Patients without cancer progression will be censored at the date of their last visit or their date of death (due to any cause). Overall cancer progression free survival rates will be summarized by using Kaplan-Meier methodology.
- **Time to untreatable metastatic lung disease control with cryoablation** is defined as the time in days from the first cryoablation procedure to the time when the metastatic lung disease cannot be treated with cryoablation. Overall time to untreatable metastatic lung disease progression rates will be summarized by using Kaplan-Meier methodology.
- **Time to untreatable metastatic lung disease control with focal therapy** is defined as the time in days from the first cryoablation procedure to the time when the metastatic lung disease cannot be treated by focal (e.g., ablation, surgery, SBRT) intervention for control of metastatic lung disease. Overall time to untreatable metastatic lung disease progression rates will be summarized by using Kaplan-Meier methodology.

Intra-procedural data

Initial cryoablation procedure information including the type of procedure, tumor size and number, cryoablation needle type and the number of each type of needle used, freeze and thaw times, procedure times, and anesthesia type will be summarized using descriptive statistics.

Physical performance and quality of life

Physical performance (KPS) and quality of life (SF-12) assessments will be made by examining the change in the baseline scores to those reported post-operatively and at follow-up visits. The KPS scale and each of the eight SF-12 domains will be summarized at each time point by descriptive statistics. Percent change from baseline for each measure will also be summarized by descriptive statistics.

Additional Data Summaries

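### Time to overall cancer progression counts any site, but scheduled follow-up looks only at the chest, so the estimate is likely to understate progression

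*Protocol*

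**What the plan says.** Protocol 5.3 lists "Time to overall cancer progression" among the other data to be assessed. Protocol 10.5.5 measures it in days from the first procedure to "cancer progression (i.e., any location of active cancer disease", and the SAP (Disease recurrence or progression) uses the same definition. The censoring rule also agrees between the two. The SAP says "Patients without cancer progression will be censored at the date of their last visit or their date of death", from any cause, and Kaplan-Meier is the planned summary.

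On ascertainment, Protocol 8.6 states that from month 1 to month 24 "follow up imaging will be chest CT or chest FDG-PET-CT". Screening uses a chest CT (7.2), and week 1 a chest X-ray or chest CT (7.4). The progression item for months 6 to 24 (7.7) is "Assessment of metastatic lung disease progression beyond the index tumor and feasibility of treatment". Months 1 and 3 (7.5, 7.6) carry the equivalent item, and the early-termination list (7.9) asks about progression of metastatic lung disease.

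On entry, Protocol 6.2.3 requires Stage 4 pulmonary metastatic disease. Criterion 6.3.2 excludes a patient only if "Patient has uncontrollable primary or metastatic disease outside of the lung", so controllable disease outside the lung is allowed.

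**The concern.** The outcome covers the whole body, while the planned observation covers the chest. A patient whose cancer progresses in, say, the liver, bone or brain has no scheduled scan or status question directed at that event. If nothing else brings it to light, the patient stays in the risk set as progression-free and is then censored at the last visit or at death. Missed events of this kind push the curve in one direction only, towards longer time to progression. A reader would take the published figure as whole-body progression in Stage 4 patients.

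A second, smaller problem lies in the wording of the event. It explains progression by reference to active disease at any location and gives no baseline, new-lesion rule or growth threshold. Sites and analysts would have to supply the rule themselves.

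**Working it through.** The documents give no figure for this outcome, so there is none to reproduce. The check is a comparison of text, followed by an illustration.

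**1. Event against ascertainment.**
- Event: progression at any location (Protocol 10.5.5; SAP).
- Scans: chest at screening, at week 1 and at months 1, 3, 6, 12, 18 and 24 (Protocol Table 1, 7.2, 7.4 to 7.7, 8.6). The FDG-PET-CT option is also limited to the chest.
- Visit items: lung disease beyond the index tumor, local recurrence, systemic cancer treatment, and local therapy to the index tumor (7.5 to 7.7). Early termination: lung progression and new cancer treatment (7.9). None asks for disease status outside the lung.
- Other sources: adverse events are recorded only if they occur within 30 days of the procedure (Section 13), and central review concerns index-tumor images (16.2). Neither fills the gap.

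**2. What happens to a missed event.** Under the censoring rule, a patient with no recorded progression is censored at the last visit or at death from any cause. A patient who dies after unrecorded extrathoracic progression is therefore censored as progression-free.

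**3. Event wording against eligibility.** Entry requires Stage 4 disease, and controllable disease outside the lung is permitted. Up to six targetable lung metastases are allowed (6.2.4), while treatment of at least one tumor is what Section 5 requires. The clock starts at the first procedure (10.5.5), yet the remaining index tumors may be treated over an 8-week window (7.3.1). Taken literally, some eligible patients therefore have active cancer at time zero. By contrast, local failure has an explicit threshold, a rise of at least 20% from the nadir (8.7.4).

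**4. Illustration of size.** These inputs are assumptions and none comes from the documents: true progression of 50% at 12 months, a constant hazard, and a share f of that hazard that is extrathoracic and wholly missed, with missed events unrelated to later chest progression.
- Hazard over 12 months: h = -ln(1 - 0.50) = 0.6931.
- Reported progression: 1 - exp(-h × (1 - f)).

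| f | h × (1 - f) | Reported at 12 months | Shortfall from 50% |
|---|---|---|---|
| 0.2 | 0.5545 | 42.6% | 7.4 points |
| 0.3 | 0.4852 | 38.4% | 11.6 points |
| 0.4 | 0.4159 | 34.0% | 16.0 points |

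If a fraction c of the extrathoracic events is found incidentally, f is replaced by f × (1 - c). With f = 0.4 and c = 0.5, the missed share is 0.2 and the reported value is 42.6%.

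**The case against.** The plan is not blind to disease outside the chest. Screening must judge criterion 6.3.2, and the SAP (Additional Data Summaries, Disease status) summarises lung or other metastatic disease. Months 1 to 24 record systemic cancer treatment, 7.8 repeats this for the whole study, and 7.9 asks for new cancer treatments and for effort to document outcome. The case report forms are not in the documents, so a missing form field is inferred from the visit lists. The outcome is descriptive, with no hypothesis test.

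Much of this stands. A reader might infer that no visit considers disease outside the lung, or that such events go entirely unrecorded. The screening judgment and the treatment items contradict that. They do not close the gap, however. A treatment item records therapy rather than the site and date of progression, and it misses progression that leads to no new treatment. Neither the screening judgment nor the SAP summary is named as the reference for progression.

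A reader might also infer that eligible patients will be scored with an event on day 0. That follows only from the literal wording. The natural reading is that the parenthesis sets the scope of locations, in contrast to the lung-only outcome listed just before it, and the censoring rule speaks of patients without progression. The literal reading would make the planned Kaplan-Meier curve pointless, and an analyst would be unlikely to adopt it. Loose wording and a missing baseline reference are what can be criticised.

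**Conclusion.** The concern holds for a non-primary, descriptive outcome. Extrathoracic progression is part of the event but is captured only incidentally, and the Kaplan-Meier estimate is likely to understate overall progression. The direction follows from the design; the size cannot be derived from the documents. The 43% to 34% range rests on the assumed 50%, the assumed 20% to 40% share, a constant hazard and no incidental capture. With some capture the shortfall is smaller.

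Two stronger conclusions are not supported. The day-0 reading and under-ascertainment are alternative readings of one sentence, so they do not add up to a compound error. Nor is the curve beyond interpretation: it can be reported with its ascertainment limit stated. Protocol 1.2 should also not be cited as saying that progression depends on the primary tumor and other organs; that passage concerns the choice of treatment. The primary 12-month local control test and the 226-tumor sample size are unaffected.

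**What to change.** - **Definition.** In the protocol and SAP, define the event as new or progressing disease at any site relative to the disease sites recorded at baseline. The disease-status item in the SAP is the natural starting point; it should name extrapulmonary sites and non-index lung disease.
- **Data.** Add one item to the follow-up and withdrawal forms: progression outside the lung since the last visit (yes/no, site, date, source), taken from routine-care records. No added scans are needed.
- **Report.** State that extrathoracic progression was ascertained from routine care without scheduled imaging.
- **Alternative.** Restrict the outcome to thoracic progression and relabel it accordingly. This needs no new data.

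The first route costs one baseline item, one item per visit and a definition change in both documents. It also needs some retrospective collection: the SAP revision history (January 2017) shows that patients with multiple lesions were already enrolled, so visits already completed would have to be filled in from records. Ascertainment would remain uneven across sites, so the bias would be reduced but not removed.
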